The PedsQL Measurement Model consists of developmentally appropriate forms for pediatric subjects  $\geq 1$  month to  $\leq 12$  months;  $\geq 13$  months to  $\leq 24$  months;  $>2$  years to  $\leq 4$  years,  $\geq 5$  years to  $\leq 7$  years,  $\geq 8$  years to  $\leq 12$  years, and  $\geq 13$  years to  $\leq 18$  years of age. Self-report is measured for pediatric subjects  $\geq 5$  years to  $\leq 18$  years of age, and parent proxy report of child health-related quality of life (HRQoL) is measured for pediatric subjects  $\geq 1$  month to  $\leq 18$  years of age.

The multidimensional PedsQL scale encompasses the essential core domains for pediatric HRQoL measurement: 1) Physical Functioning/Symptoms, 2) Emotional Functioning, 3) Social Functioning, and 4) Cognitive/School Functioning. The PedsQL assessment is retrospective to the prior month, and individual items are scored using a 5-point Likert scale (never, almost never, sometimes, often, or always). A total health summary score is calculated from the sum of the raw scores of the individual items, with higher scores indicating higher HRQoL.

*Clinical Study Protocol, Section 6.4 (Health care resource use) was newly added as follows:*

For health care resource use parameters, the following will be evaluated: concomitant AEDs, medical procedures, health care provider consultations not related to study, and hospitalizations not related to study. Health care resource use parameters will be collected according to the tabular schedule of study procedures, [Section 16.1](#).

*Clinical Study Protocol, Section 8.4 section heading. Original text:*

Other safety measurements

*Was revised as follows:*

Other measurements

*Clinical Study Protocol, Section 8.4.2 (Neurological examination), final sentence. Original text:*

The investigator or subinvestigator is responsible for confirming the diagnosis of partial-onset seizures.

*Was revised as follows:*

The investigator or subinvestigator is responsible for confirming the diagnosis of partial-onset seizures or other epilepsy syndrome.

*Clinical Study Protocol, Section 8.4.6 (Assessment of suicidality), the following paragraph was added:*

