The full-analysis set will be used for the analysis of seizure data and will consist of all subjects in the SS, who have at least 1 completed post-Baseline seizure diary.

*Clinical Study Protocol, Section 12.1.5 (Handling of protocol violators, drop-outs, and missing values). Original text, first paragraph:*

All data will be used to their maximum possible extent, but without any imputations for missing data for any parameter. Protocol deviations will be assessed during data review by a panel consisting of the study manager, the study biostatistician, a representative of the monitoring team, and other appropriate study team members.

*Was revised as follows:*

All data will be used to their maximum possible extent, but without any imputations for missing data for any parameter. Important protocol deviations will be reviewed as part of the ongoing data cleaning process and data evaluation. All important deviations will be identified and documented prior to database lock to confirm exclusion from analysis sets.

*Clinical Study Protocol, Section 12.2 (Determination of sample size). The following final paragraph was added:*

Beginning with Protocol Amendment 6, up to 75 eligible pediatric subjects  $\geq 4$  years to  $< 17$  years of age who have participated in EP0060 will be permitted to enroll into SP848.

*Clinical Study Protocol, Section 15 (References). The following references were added:*

Clinical Global Impression of Change, the Caregiver Global Impression of Change, quality of life assessments (Pediatric Quality of Life Inventory [PedsQL™]).  
<http://www.pedsql.org/PedsQL-CostStructure.pdf> and <http://plaza.umin.ac.jp/qol-research/>. Accessed on 10 July 2014.

Cognitive function assessments (Behavior Rating Inventory of Executive Function® [BRIEF®]/BRIEF® Preschool Version [BRIEF® P].  
<http://www4.parinc.com/Products/PermsLicensing.aspx?id=6> and  
<http://www4.parinc.com/products/PermsLicensing.aspx?id=8>. Accessed 10 July 2014.

Food and Drug Administration. Guidance for Industry. Drug-induced liver injury: premarketing clinical evaluation. US Dept of Health and Human Services, Center for Drug Evaluation and Research, Center for Biologics Evaluation and Research, 07/2009.

Kyoto International; Social Welfare Exchange Centre (KISWEC). Achenbach Child Behavior Checklist (CBCL) for children 18 months and older.  
<http://www.kiswec.com/aseba%20-%20order.html>. Accessed 10 July 2014.

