In cases where subjects cannot return to the clinic, and it will not be possible to dispense a new seizure diary, subjects will be instructed to continue recording of seizures in a manner that is mutually agreed with the investigator (eg, hand-written notes, recording on a smart device). Any recording of seizures in a manner outside of the study seizure diary must be carefully documented in the source medical records (copies/print-screen printouts of these recordings will be brought to and retained at the site).

*Clinical Study Protocol, Section 6.2.1 (Clinical Global Impression of Change). Original text, first paragraph:*

The Clinical Global Impression of Change will be completed according to the tabular schedule of study procedures, [Section 16.1](#).

*Was revised as follows:*

The Clinical Global Impression of Change will be assessed at least once per year and be completed according to the tabular schedule of study procedures, [Section 16.1](#).

*Clinical Study Protocol, Section 6.2.2 (Caregiver Global Impression of Change). Original text, first paragraph:*

The Caregiver Global Impression of Change will be completed according to the tabular schedule of study procedures, [Section 16.1](#).

*Was revised as follows:*

The Caregiver Global Impression of Change will be assessed at least once per year and be completed according to the tabular schedule of study procedures, [Section 16.1](#).

*Clinical Study Protocol, Section 6.3 (Pediatric Quality of Life Inventory). Original text, first paragraph:*

The PedsQL is a validated instrument that consists of generic core scales suitable for use with pediatric populations, including those with acute or chronic health conditions (Varni et al, 2001; Varni et al, 2011). The PedsQL will be administered according to the tabular schedule of study procedures, [Section 16.1](#).

*Was revised as follows:*

The PedsQL is a validated instrument that consists of generic core scales suitable for use with pediatric populations, including those with acute or chronic health conditions (Varni et al, 2001; Varni et al, 2011). The PedsQL will be completed up to two times per year and will be administered according to the tabular schedule of study procedures, [Section 16.1](#).

*Clinical Study Protocol, Section 8.1.10 (Occurrence of COVID-19) was newly added as follows:*

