#### **12.1.4.2.2 PedsQL**

The PedsQL score and change from Baseline scores will be analyzed in a descriptive manner. Baseline is defined as Visit 1 for subjects from SP847 or other epilepsy studies. Baseline values for subjects who enroll directly into SP848 will be taken from the Screening Visit.

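### Section 6.3 makes the PedsQL total a raw item sum, which depends on the number of items answered and is on a common scale across the six age forms only if their lengths are equal

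*Protocol*

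**What the plan says.** Section 6.3, added by Protocol Amendment 5, describes the response format: "individual items are scored using a 5-point Likert scale (never, almost never, sometimes, often, or always". It names four domains: "1) Physical Functioning/Symptoms, 2) Emotional Functioning, 3) Social Functioning, and 4) Cognitive/School Functioning". The total is then defined: "A total health summary score is calculated from the sum of the raw scores of the individual items, with higher scores indicating higher HRQoL". The section assigns no numbers to the five categories and gives no item wording, item counts or rule for unanswered items.

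The same section says: "The PedsQL Measurement Model consists of developmentally appropriate forms for pediatric subjects". Six age bands follow, with changes after 12 months, after 24 months, and at 5, 8 and 13 years. Self-report starts at age 5, and parent proxy report covers all ages.

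Protocol Amendment 8 shows only the first paragraph of Section 6.3 as revised, adding that "The PedsQL will be completed up to two times per year and will be administered according to the tabular schedule of study procedures". The scoring sentence is therefore taken as current.

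Section 12.1.5, as revised in Amendment 6, says: "All data will be used to their maximum possible extent, but without any imputations for missing data for any parameter". Section 12.1.4.2.2 (Amendment 8) says: "The PedsQL score and change from Baseline scores will be analyzed in a descriptive manner". It does not say how self-report and proxy report, or different age forms, are to be handled.

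**The concern.** A sum of raw item scores is a sound measure of change only if the number of items behind it stays fixed and every item points the same way. The text shown secures neither.

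- **Blanks.** A parent who skips two questions at Week 52 gives a lower total than at Baseline, although nothing about the child has changed. The alternative is to drop that child's total. Which of the two applies is left open.
- **Age forms.** Children are followed for up to 96 weeks after Visit 1, so many will move to another form. If the forms differ in length, the raw total changes for that reason alone.
- **Orientation.** The responses run from *never* to *always*, and one domain is named for symptoms. A symptom that is always present is bad, so the higher-is-better statement needs a reversal that the text does not mention.

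The study has no control arm, so an artefact in change from Baseline is not cancelled by a comparison group.

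**Working it through.** The plan gives no PedsQL figure to reproduce. The arithmetic below shows how the stated rule behaves. Section 6.3 gives neither item counts nor numeric codes, so the item number *k* and the codes 0 to 4 are assumptions.

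**1. Blank items.** Suppose each answered item scores *a* and *m* of *k* items are left blank. The sum goes from *k·a* to *(k − m)·a*, a relative change of *−m/k* whatever the value of *a*. The mean of the answered items stays at *a*. With *a* = 3:

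| Items | Blank | Sum, complete | Sum, with blanks | Change | Mean |
|---|---|---|---|---|---|
| 20 | 1 | 60 | 57 | −5% | 3.0 |
| 20 | 2 | 60 | 54 | −10% | 3.0 |
| 20 | 5 | 60 | 45 | −25% | 3.0 |
| 30 | 1 | 90 | 87 | −3.3% | 3.0 |
| 30 | 5 | 90 | 75 | −16.7% | 3.0 |

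If the total is instead set to missing whenever an item is blank, no false change appears, but the child's other answers are not used in the total. That sits poorly with the instruction in Section 12.1.5 to use data as fully as possible.

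**2. Age forms.** At the same mean answer *a*, moving from a form with *k₁* items to one with *k₂* items changes the sum by *a·(k₂ − k₁)*. With *a* = 3:

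- 20 to 20 items: 0
- 20 to 25 items: 3 × 5 = +15, from 60 to 75
- 40 to 20 items: 3 × (−20) = −60, from 120 to 60

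The effect is zero if all forms have equal length. The text shown does not settle which case applies.

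**3. How many children change form.** The last scheduled visit is Week 96, and 96 × 7 / 365.25 = 1.84 years. Direct enrollers are 4 to 17 years old. Take entry age as uniform from 4 to <18 (assumption), a span of 14 years. A boundary is crossed by those entering at:

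- 4 to 5 years: 1.00 year of entry ages
- 6.16 to 8 years: 1.84
- 11.16 to 13 years: 1.84

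The total is 4.68, and 4.68 / 14 = 33%. The same calculation over 1 month to <18 years, which covers children arriving from other studies, gives 42%. Baseline for direct enrollers is the Screening Visit, before titration, so their true interval is a little longer than 96 weeks and 33% is slightly low. These are shares of children who change form, not shares whose score is distorted.

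**4. Direction.** A symptom item improves from *often* to *almost never*.

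- Codes in the listed order (*never* = 0 to *always* = 4): 3 to 1, a change of −2 per item.
- Reversed codes: 1 to 3, a change of +2 per item.

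Only the reversed coding agrees with the stated direction for such an item. The text does not say which coding is used.

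**5. After the fix.** With reversed codes and a mean over answered items, the same answers give 3.0 out of 4 whatever the number of blanks or the form length. The improvement in step 4 then moves the score up by 2 out of 4 per item.

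**The case against.** The strongest reply is that this is scoring detail. A protocol commonly leaves item coding and missing-item rules to the SAP or the instrument's manual, and Section 6.3 calls the PedsQL validated and cites sources. Saying that a total is calculated from a sum does not exclude a later average or rescaling. This reply stands for the bare absence of a missing-item rule. It does not remove the point, because the protocol states a rule, the raw sum, and a better one is available at no cost in data.

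A reader might infer three stronger things, none of which the documents support:

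- *Symptom items score in the wrong direction.* No numeric codes are given, and the protocol itself fixes higher as better. Reversed codes satisfy that. What is shown is an unstated reversal.
- *The total shifts with the child's age form.* That requires forms of different length, and no item counts are given. The 33% shows how many children are exposed to the question, not that any score moves.
- *Change from Baseline is the only PedsQL result.* Section 12.1.4.2.2 also summarises the score itself.

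Two further objections are fair. Averaging the answered items implicitly gives each blank the child's own mean, so it has to be reconciled with the no-imputation rule; the fix does this. Restricting the analysis to parent proxy would set aside self-report, which none of these problems requires. Finally, only the second part of the protocol was available, so the consolidated Section 6.3 should be checked for text on orientation.

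**Conclusion.** The point holds as a low-severity correction to a stated scoring rule. The blank-item problem follows directly from combining Section 6.3 with Section 12.1.5: each blank changes the total by −1/*k* or makes it missing, which is −10% for 2 blanks of 20. The percentage rests on the assumed item count; the dependence on blanks does not.

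The age-form problem is conditional on forms of unequal length. About a third of direct enrollers would be exposed to it under uniform entry ages. The direction is ambiguous and should be stated.

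The consequence is limited. Section 4.2.3.3 lists PedsQL among the other efficacy variables, its analysis is descriptive, and no test or sample size depends on it. The primary safety variables are unaffected.

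**What to change.** **Section 6.3.** Replace the raw-sum sentence with a rule of this kind: each item is oriented so that a higher value means better quality of life and is rescaled to a common range; the total is the mean of the answered items; it is calculated only when the minimum number of items required by the instrument's scoring manual has been answered. Cite the manual for the item codes.

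**Section 12.1.5.** Add that this per-item mean is not treated as imputation.

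**Section 12.1.4.2.2.** State that change from Baseline is taken within the same respondent type, self-report or parent proxy, and that children who change age form are shown separately. A common range removes the effect of form length, but it does not make different item content equivalent, so the separate display is still needed.

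The cost is a few sentences and a changed derivation program. No additional data collection is needed.

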**Table 1. Schedule of study procedures for SP848 (Year 1)**

Study SP848	Year 1												Safety Follow-Up	
	V1 b	TC c	V2	V3	V4	V5	V6	V7	V8	V9	ETV d	Unsch Visit e	Final Visit f	
Visita														
Weeks in study	0		4	8	12	20	28	36	44	52				
Informed Consent	X													
Inclusion/exclusion criteria	X													
Medical history update	X													
Concomitant medications	X h	X	X	X	X	X	X	X	X	X	X	X	X	X
Concomitant AEDs	X h	X	X	X	X	X	X	X	X	X	X	X	X	X
Physical exam (complete)	X h					X				X	X			X
Physical exam (brief)			X	X	X		X	X	X			X		
Neurological exam (complete)	X h					X				X	X			X
Neurological exam (brief)			X	X	X		X	X	X			X		
12-lead ECG i	X h		X				X			X	X	X	X	X
Blood pressure and pulse	X h		X	X	X	X	X	X	X	X	X	X	X	X
Body weight and height	X h		X	X	X	X	X	X	X	X	X	X	X	X
Clinical chemistry and hematology blood sample	X h		X			X		X		X	X			X
Endocrinology blood sample	X h					X				X	X			X
Blood sample for LCM PK j	X h		X			X		X		X	X			
Blood sample for concomitant AEDs j	X h		X			X		X		X	X			
Urinalysis (subjects aged 5 to 17 years)	X h					X				X	X			X
Pregnancy test k	X h,S		X U	X S		X S								
Tanner Stage l	X h								X			X		
Clinical GIC	X h					X				X	X			
Caregiver GIC	X h					X				X	X			
Palatability and ease of use questionnaire							X			X	X			
Dispense LCM	X		X	X	X	X	X	X	X	X	X m	X n		
LCM return/compliance			X	X	X	X	X	X	X	X	X	X n	X	

**Table 1. Schedule of study procedures for SP848 (Year 1)**

Study SP848	Year 1												Safety Follow-Up	
	V1 b	TC c	V2	V3	V4	V5	V6	V7	V8	V9	ETV d	Unsch Visit e	Final Visit f	
Visita														
Weeks in study	0		4	8	12	20	28	36	44	52				
Dispense diary	X		X	X	X	X	X	X	X	X	X			
Diary assessment			X	X	X	X	X	X	X	X	X	X	X	
C-SSRS o	X h		X	X	X	X	X	X	X	X	X	X p	X	
Achenbach CBCL	X					X				X	X			
Bayley-III scales	X					X				X	X			
BRIEF-P/BRIEF	X					X				X	X			
PedsQL	X					X				X	X			
AE reporting q	X h	X	X	X	X	X	X	X	X	X	X	X	X	
Health care resource use	X		X	X	X	X	X	X	X	X	X	X	X	

AE=adverse event; AED=antiepileptic drug; C-SSRS=Columbia-Suicide Severity Rating Scale; ECG=electrocardiogram; ETV=Early Termination Visit; GIC=Global Impression of Change; LCM=lacosamide; PK=pharmacokinetics; TC=telephone contact; S=serum; U=urine; Unsch=Unscheduled; V=Visit

a A time window of  $\pm 7$  days relative to Visit 1 is applicable for all scheduled visits and telephone contacts (with the exception of the Safety Follow-Up telephone contact).

b For subjects who have participated in SP847 (or other LCM pediatric clinical studies in epilepsy), Visit 1 is also the last visit of the primary study. At Visit 1, the informed consent will be signed (and assent, if applicable) and eligibility assessed, the medical history will be updated, body weight and height and concomitant medications including AEDs will be recorded, AEs will be assessed, and the subject diary and LCM dispensed.

c Telephone contacts are scheduled during the following weeks during Year 1: Weeks 2, 6, 10, 16, 24, 32, 40, and 48.

d An Early Termination Visit must be completed for all subjects who prematurely discontinue from the study.

e If an Unscheduled Visit is needed, then the assessments noted will be performed. Additional assessments can be performed at the investigator's discretion. If the LCM dose is decreased between scheduled clinic visits due to an AE, or if a LCM dose increase is required between scheduled clinic visits, the subject must return for an Unscheduled Visit. Height will not be recorded at an Unscheduled Visit.

f Subjects who complete the study or withdraw prematurely from the study, and who discontinue use of LCM (ie, taper), should complete the Final Visit 2 weeks after the final dose of study medication.

g This TC occurs 28 to 35 days after the last dose of LCM.

h For subjects enrolling from SP847 or other LCM pediatric clinical studies in epilepsy, assessments should have been done as part of the last visit of the primary study. For subjects enrolling directly into SP848, these assessments should be completed at Visit 1.

i All subjects will be required to have a 12-lead ECG (2 interpretable recordings) conducted at LCM Cmax 1 week after an initial LCM dose increase to a LCM dose level that is  $\geq 8$ mg/kg/day or a new concomitant AED is introduced. This ECG can be conducted at an Unscheduled Visit, if necessary. Subjects having a LCM dose increase to  $\geq 8$ mg/kg/day will be required to arrive at the clinic prior to taking their morning dose of LCM. Subjects will be administered their morning LCM dose by study personnel at the clinic so that an ECG (2 interpretable recordings approximately 20 to 30 minutes apart prior to vital signs assessment) can be performed 30 minutes to 1 hour after the administration of LCM (ie, at LCM steady state Cmax).

- j Blood samples may be drawn at any time post-dosing with LCM.
- k For female subjects of childbearing potential, serum pregnancy tests will be performed at Visit 1, the Early Termination Visit, and the Final Visit. Urine pregnancy tests will be performed at Visits 2, 3, 4, 5, 6, 7, 8, and 9.
- l The Tanner Stage will be performed only for subjects who are pubescent at Visit 1 or who will enter puberty during the course of the study.
- m Lacosamide for taper will be dispensed only for subjects who achieve a dose of LCM  $\geq 6$ mg/kg/day (oral solution [syrup]) or  $\geq 300$ mg/day (tablet). It is recommended that the LCM dose be tapered gradually in weekly decrements of 4mg/kg/day (oral solution [syrup]) or 200mg/day (tablet). A slower taper of 2mg/kg/day (oral solution [syrup]) or 100mg/day (tablet) is permitted, if medically necessary. In case of an emergency, a faster taper is permitted after discussion with the medical monitor, whenever possible.
- n As applicable
- o For all subjects  $\geq 6$  years of age already enrolled, the “already enrolled” version should be completed at the next clinic visit, and the “since last visit” version should be completed thereafter.
- p The C-SSRS assessment should be completed if the Unscheduled Visit is due to an AE.
- q Ongoing AEs from the primary study will be followed, as well as recording of new AEs during the current study.

**Table 2.** Schedule of study procedures for SP848 (Year 2)

Study SP848	Year 2								Safety Follow-Up
Visit a	V10	TC b	V11	V12	V13/TermV	ETV c	Unsch Visit d	Final Visit e	TC f
Weeks in study	60		72	84	96				
Concomitant medications	X	X	X	X	X	X	X	X	X
Concomitant AEDs	X	X	X	X	X	X	X	X	X
Physical exam (complete)					X	X		X	
Physical exam (brief)	X		X	X			X		
Neurological exam (complete)					X	X		X	
Neurological exam (brief)	X		X	X			X		
12-lead ECG g			X		X	X	X	X	
Blood pressure and pulse	X		X	X	X	X	X	X	
Body weight and height	X		X	X	X	X	X	X	
Clinical chemistry and hematology blood sample	X		X	X	X	X			X
Endocrinology blood sample				X			X		X
Blood sample for LCM PK h	X		X	X	X	X			
Blood sample for concomitant AEDs h	X		X	X	X	X			
Urinalysis (subjects aged 5 to 17 years)			X		X	X			X
Pregnancy test i	X U		X U	X U	X U	X S		X S	
Tanner Stage j					X	X			
Clinical GIC			X		X	X			
Caregiver GIC			X		X	X			
Palatability and ease of use questionnaire			X		X	X			
Dispense LCM	X		X	X	X k	X k	X l		
LCM return/compliance	X		X	X	X	X	X l	X	
Dispense diary	X		X	X	X	X			

**Table 2.** Schedule of study procedures for SP848 (Year 2)

Study SP848	Year 2								Safety Follow-Up
Visit a	V10	TC b	V11	V12	V13/TermV	ETV c	Unsch Visit d	Final Visit e	TC f
Weeks in study	60		72	84	96				
Diary assessment	X		X	X	X	X	X	X	
C-SSRS m	X		X	X	X	X	X n	X	
Achenbach CBCL			X		X	X			
Bayley-III scales			X		X	X			
BRIEF-P/BRIEF			X		X	X			
PedsQL			X		X	X			
AE reporting	X	X	X	X	X	X	X	X	X
Health care resource use	X		X	X	X	X	X	X	

AE=adverse event; AED=antiepileptic drug; C-SSRS=Columbia-Suicide Severity Rating Scale; ECG=electrocardiogram; ETV=Early Termination Visit; GIC=Global Impression of Change; LCM=lacosamide; PK=pharmacokinetics; S=serum; TC=telephone contact; TermV=Termination Visit; U=urine; Unsch=Unscheduled; V=Visit

a A time window of  $\pm 7$  days relative to Visit 1 is applicable for all scheduled visits and telephone contacts (with the exception of the Safety Follow-Up telephone contact).

b Telephone contacts are scheduled during the following weeks during Year 2: Weeks 66 and 78.

c An Early Termination Visit must be completed for all subjects who prematurely discontinue from the study.

d If an Unscheduled Visit is needed, then the assessments noted will be performed. Additional assessments can be performed at the investigator's discretion. If the LCM dose is decreased between scheduled clinic visits due to an AE, or if a LCM dose increase is required between scheduled clinic visits, the subject must return for an Unscheduled Visit. Height will not be recorded at an Unscheduled Visit.

e Subjects who complete the study or withdraw prematurely from the study, and who discontinue use of LCM (ie, taper), should complete the Final Visit 2 weeks after the final dose of study medication.

f This TC occurs 28-35 days after the last dose of LCM.

g All subjects will be required to have a 12-lead ECG (2 interpretable recordings) conducted at LCM  $C_{max}$  1 week after an initial LCM dose increase to a LCM dose level that is  $\geq 8$  mg/kg/day or a new concomitant AED is introduced. This ECG can be conducted at an Unscheduled Visit, if necessary. Subjects having a LCM dose increase to  $\geq 8$  mg/kg/day will be required to arrive at the clinic prior to taking their morning dose of LCM. Subjects will be administered their morning LCM dose by study personnel at the clinic so that an ECG (2 interpretable recordings approximately 20 to 30 minutes apart prior to vital signs assessment) can be performed 30 minutes to 1 hour after the administration of LCM (ie, at LCM steady-state  $C_{max}$ ).

h Blood samples may be drawn at any time post-dosing with LCM.

i For female subjects of childbearing potential, serum pregnancy tests will be performed at the Early Termination Visit and at the Final Visit. Urine pregnancy tests will be performed at Visits 10, 11, 12, and 13.

- j The Tanner Stage will be performed only for subjects who are pubescent at Visit 1 or who will enter puberty during the course of the study.
- k Lacosamide for taper will be dispensed only for subjects who achieve a dose of LCM  $\geq 6$ mg/kg/day (oral solution [syrup]) or  $\geq 300$ mg/day (tablet). It is recommended that the LCM dose be tapered gradually in weekly decrements of 4mg/kg/day (oral solution [syrup]) or 200mg/day (tablet). A slower taper of 2mg/kg/day (oral solution [syrup]) or 100mg/day (tablet) is permitted, if medically necessary. In case of an emergency, a faster taper is permitted after discussion with the medical monitor, whenever possible.
- l As applicable.
- m For all subjects  $\geq 6$  years of age already enrolled, the “already enrolled” version should be completed at the next clinic visit, and the “since last visit” version should be completed thereafter.
- n The C-SSRS assessment should be completed if the Unscheduled Visit is due to an AE.

**Table 3. Schedule of study procedures for SP848 (Screening Visit and Titration Visits, subjects enrolling directly into SP848)**

Study SP848	Screening	Titration Visits					
		Titration Visit 1	Titration Visit 2	Titration Visit 3	Titration Visit 4	Titration Visit 5	Titration Visit 6
Visit	Screening Visit						
Informed Consent	X						
Inclusion/exclusion criteria	X						
Medical history	X						
Seizure history	X						
Concomitant medications	X	X	X	X	X	X	X
Concomitant AEDs	X	X	X	X	X	X	X
Physical exam (complete)	X						
Physical exam (brief)		X	X	X	X	X	X
Neurological exam (complete)	X						
Neurological exam (brief)		X	X	X	X	X	X
12-lead ECG a	X	X	X	X	X	X	X
Blood pressure and pulse	X	X	X	X	X	X	X
Body weight	X	X	X	X	X	X	X
Height	X						
Clinical chemistry and hematology blood sample	X				X		
Endocrinology blood sample	X				X		
Urinalysis (subjects aged 5 to 17 years)	X				X		
Pregnancy test b	X						
Tanner Stage	X						
Clinical GIC							
Caregiver GIC							
Dispense LCM		X	X	X	X	X	X
LCM return/compliance		X	X	X	X	X	X
Dispense diary	X	X	X	X	X	X	X
Diary assessment		X	X	X	X	X	X
C-SSRS c	X	X	X	X	X	X	X
Achenbach CBCL	X						

**Table 3. Schedule of study procedures for SP848 (Screening Visit and Titration Visits, subjects enrolling directly into SP848)**

Study SP848	Screening	Titration Visits					
		Titration Visit 1	Titration Visit 2	Titration Visit 3	Titration Visit 4	Titration Visit 5	Titration Visit 6
Visit	Screening Visit						
Bayley-III scales	X						
BRIEF-P/BRIEF	X						
PedsQL	X						
AE reporting	X	X	X	X	X	X	X
Health care resource use	X	X	X	X	X	X	X

AE=adverse event; AEDs=antiepileptic drugs;  $C_{\max}$ =maximum plasma concentration; C-SSRS=Columbia-Suicide Severity Rating Scale;

ECG=electrocardiogram; GIC=Global Impression of Change; LCM=lacosamide

a All subjects will be required to have a 12-lead ECG (2 interpretable recordings) conducted at LCM  $C_{\max}$  1 week after an initial LCM dose increase to a LCM dose level that is  $\geq 8\text{mg/kg/day}$  or a new concomitant AED is introduced. This ECG can be conducted at an Unscheduled Visit, if necessary. Subjects having a LCM dose increase to  $\geq 8\text{mg/kg/day}$  will be required to arrive at the clinic prior to taking their morning dose of LCM. Subjects will be administered their morning LCM dose by study personnel at the clinic so that an ECG (2 interpretable recordings approximately 20 to 30 minutes apart prior to vital signs assessment) can be performed 30 minutes to 1 hour after the administration of LCM (ie, at LCM steady state  $C_{\max}$ ).

b For female subjects of childbearing potential, serum pregnancy tests will be performed at the Screening Visit.

c For all subjects  $\geq 6$  years of age already enrolled, the “already enrolled” version should be completed at the next clinic visit, and the “since last visit” version should be completed thereafter.

*Clinical Study Protocol, Section 16.3 (Declaration and signatures of person responsible for the study). The signature block for the Clinical Project Manager was updated as follows:*

Clinical Project Manager

[REDACTED], RN, MSN

\_\_\_\_\_  
Date / Signature

REDACTED COPY

This document cannot be used to support any marketing authorization application and any extensions or variations thereof.

## 17.6 PROTOCOL AMENDMENT 6

